6.9. Prior and Concomitant Therapy

Any medication or vaccine (including OTC or prescription medicines, recreational drugs, vitamins, and/or herbal supplements) or other specific categories of interest (see below) that the participant is receiving at the time of enrollment or receives during the study must be recorded along with:

- Reason for use.
- Dates of administration including start and end dates.
- Dosage information including dose and frequency.

Specific categories of interest:

- All prior medications (including any prescription or OTC medications, vaccines, or blood products) taken by the participant within the 28 days before providing informed consent.
- Any licensed seasonal influenza vaccine administered in the prior 12 months.
- Any licensed/authorized or investigational COVID-19 vaccine administered at any time before study intervention administration.
- Any vaccine (authorized or investigational) administered in the prior 12 months. For authorized influenza vaccines, detailed information regarding which vaccine was administered should be provided if available.

The medical monitor should be contacted if there are any questions regarding concomitant or prior therapy.

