- Any investigational or nonregistered product (drug or vaccine) other than the study interventions used during the study period.
- A nonstudy vaccine (including authorized or approved vaccines for the prevention of COVID-19 regardless of the type of vaccine) administered during the period from 28 days before through 21 days after each study injection (until Day 43).

mRNA-1345

- Nonstudy influenza or RSV vaccine at any time during the study.
- Igs and/or any blood products administered during the study period.

• Medications that suppress the immune system.

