- b) Study day on or after the date of the Day 1 injection but before the Day 22 injection (if applicable) will be calculated as: date of assessment/event date of the Day 1 injection + 1;
- c) Study day on or after the date of the Day 22 injection will be calculated as: date of assessment/event date of the Day 22 injection + 1; if study day is on the same day as the Day 22 injection, date and time will be compared with the Day 22 injection date and time. If it is prior to the Day 22 injection, then study day is calculated as bullet point b); if it is after the Day 22 injection or the time is missing or not available then study day is calculated as: date of assessment/event date of the Day 22 injection + 1.

For GMT and GMC calculation, antibody values reported as below the LLOQ will be replaced by $0.5 \times \text{LLOQ}$ and antibody values greater than the ULOQ will be converted to the ULOQ.

Unscheduled visits: Unscheduled visit measurements will be included in analysis as follows:

- In the derivation of baseline measurements.
- In scheduled visit windows per specified visit windowing rules.
- In individual participant data listings as appropriate.

Visit windowing rules: The analysis visit windows for protocol-defined visits are provided in Appendix B.

Incomplete/missing data:

- Imputation rules for missing dates of prior/concomitant medications and non-study vaccinations are provided in Appendix C.
- Imputation rules for missing dates of prior/concomitant procedures are provided in Appendix D.
- Imputation rules for missing AE dates are provided in Appendix E.
- Other incomplete/missing data will not be imputed, unless specified otherwise.

Treatment groups:

The following treatment groups will be used for summary purposes:

- D1: Fluzone HD+mRNA-1345 (μg) and D22: placebo
- D1: Fluzone HD+placebo and D22: mRNA-1345 (μg)

If a subject receives any dose of mRNA-1345 on Day 1, regardless of the treatment group the subject is randomized to, the subject will be included in the actual treatment group "D1: Fluzone HD+mRNA-1345 (µg) and D22: placebo" for safety and reactogenicity analyses.

All analyses and data summaries/displays for disposition, demographics and baseline characteristics, safety and immunogenicity will be provided by treatment group using appropriate analysis population, unless otherwise specified. Local solicited adverse reactions will be also summarized by injection content (mRNA-1345, Placebo and Fluzone HD).

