6.2.4. Prior and Concomitant Medications

Any medication or vaccine (including OTC or prescription medicines, recreational drugs, vitamins, and/or herbal supplements) or other specific categories of interest that the participant is receiving at the time of enrollment or receives during the study will be recorded in the participant's eCRF. Specific categories of interest are detailed in the section 6.9 of the study protocol.

Prior and concomitant medications will be coded using the World Health Organization (WHO) drug dictionary (WHO-DD). The summary of concomitant medications will be based on the Safety Set. Imputation rules for missing/partial dates for medications is detailed in Appendix C.

For analysis purpose, a medication taken prior to the Day 1 injection date, regardless of whether the end date is before or after the injection date, is defined as "prior"; if the medication is taken on or after the Day 1 injection date through Month 6/EoS visit, then it is considered "concomitant", regardless of whether the start date is before or after the injection date.

An overall summary table of concomitant medications and non-study vaccinations will be provided to present the number and percentage of participants who take the following:

- Any concomitant medications and non-study vaccinations within 7 days post any injection
- Any concomitant medications and non-study vaccinations within 21 days post any injection
- Any non-study vaccinations within 7 days post any injection
- Any non-study vaccinations within 21 days post any injection
- Any prophylactic antipyretics or analgesics medication within 21 days post any injection
- Any antipyretic or analgesic medication within 21 days post any injection

A summary table of concomitant medications and non-study vaccinations within 21 days post any injection will be provided by ATC level 2 and PT. PT will be displayed in descending order of frequency of the "D1: Fluzone HD+mRNA-1345 (µg) and D22: placebo" group. A separate summary table of non-study vaccinations within 7 days post any injection will be also provided by PT.

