9.3. Appendix C Imputation Rules for Missing Dates of Prior/Concomitant Medications

Imputation rules for missing or partial start/stop dates of medication are defined below:

- 1. Missing or partial medication start date:
 - If only Day is missing, use the first day of the month, unless:
 - The medication end date is on/after the date of the injection or is missing/partial AND the start month and year of the medication coincide with the start month and year of the injection. In this case, use the date of the injection.
 - If Day and Month are both missing, use the first day of the year, unless:
 - The medication end date is on/after the date of the injection or is missing/partial AND the start year of the medication coincide with the start year of the IP injection. In this case, use the date of the injection.
 - If Day, Month, and Year are all missing, the date will not be imputed, but the medication will be treated as though it began prior to the injection for purposes of determining if status as prior or concomitant.
- 2. Missing or partial medication stop date:
 - If only Day is missing, use the earliest date of (last day of the month, study completion, discontinuation from the study, or death).
 - If Day and Month are both missing, use the earliest date of (last day of the year, study completion, discontinuation from the study, or death).
 - If Day, Month, and Year are all missing, the date will not be imputed, but the medication will be flagged as a continuing medication.

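### SAP Appendix C can re-date a vaccine reported as given before Day 1 to the injection day, so that it enters the post-injection vaccination summaries

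*SAP*

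**What the plan says.** SAP 6.1 makes the link explicit: "Imputation rules for missing dates of prior/concomitant medications and non-study vaccinations are provided in Appendix C". Appendix C has no separate paragraph for vaccines.

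For a start date known only by year, Appendix C begins with a default: "If Day and Month are both missing, use the first day of the year, unless". The exception has two conditions. The first concerns the end date: "The medication end date is on/after the date of the injection or is missing/partial AND the start year of the medication". The second concerns the year, and gives the result: "the start year of the medication coincide with the start year of the IP injection. In this case, use the date of the injection". A parallel exception covers a start date with only the day missing, where month and year must both match the injection. A start date that is wholly missing is handled the other way: "the date will not be imputed, but the medication will be treated as though it began prior to the injection".

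SAP 6.2.4 treats anything taken on or after the date of the Day 1 injection as concomitant. One of its summary rows is "Any non-study vaccinations within 7 days post any injection". There is a matching 21-day row, combined rows for medications and vaccinations together, and a 7-day vaccination table by preferred term.

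Protocol 6.9 makes earlier vaccines part of the data to be recorded: "Any vaccine (authorized or investigational) administered in the prior 12 months". It also asks for licensed influenza vaccine in the prior 12 months and for COVID-19 vaccine at any earlier time.

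**The concern.** Moving a partial start date to the injection day is a cautious choice for a drug that may still be in use. A vaccination happens on one day. If it was reported at screening as already given, the record shows that it preceded Day 1, and the rule discards that information.

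The result also conflicts with eligibility. Exclusion 16 bars vaccines in the 28 days before a study injection, and exclusion 17 bars seasonal influenza vaccine in the 6 months before Day 1. A participant who met both could still appear in the tables as vaccinated on Day 1. True counts in these tables should be low by design, so even a few false entries would change how they read.

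**Working it through.** The plan states no figure for this rule, so there is nothing to reproduce. I applied the text literally to test records.

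**Inputs.** Start-date and stop-date rules: SAP Appendix C. Status and tabulation: SAP 6.2.4. Vaccine exclusion windows: protocol 5.2, criteria 16 and 17. The Day 1 dates below are assumptions.

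**Rule for a year-only start.** Let J be the injection date, Y the recorded start year and E the end date.
- Start = J if year(J) = Y and E is missing, partial or ≥ J.
- Start = 1 January of Y otherwise.

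**Results with Day 1 on 15 Nov 2023.**

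| Recorded start | End date | Start assigned | Consequence |
|---|---|---|---|
| 2023 | missing | 15 Nov 2023 | concomitant; in 7-day and 21-day counts |
| 2023 | 2023 only | 15 Nov 2023 | concomitant; in 7-day and 21-day counts |
| 2023 | 10 Jan 2023 | 1 Jan 2023 | prior |
| 2022 | missing | 1 Jan 2022 | not re-dated |
| wholly missing | – | none | start treated as before the injection |

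Knowing the year therefore gives a worse start status for an old vaccine than knowing nothing.

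**End date.** A year-only end date is itself imputed to the earliest of 31 December, study completion, discontinuation or death. For a 2023 record that falls after Day 1. The end-date condition is met whether it is tested before or after stop-date imputation. Correcting the start date alone would therefore leave the record running past Day 1.

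**Room for such records.** A same-year vaccine outside the 28-day window must fall at least 29 days before Day 1. The number of possible days is the day-of-year of Day 1 minus 29:
- 1 Sep: 244 − 29 = 215
- 1 Oct: 274 − 29 = 245
- 15 Nov: 319 − 29 = 290
- 31 Dec: 365 − 29 = 336
- 15 Jan: 15 − 29 < 0, so none

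With autumn dosing, most of the year is open. With dosing in mid-January, no eligible same-year record can exist. For influenza vaccine the 6-month criterion narrows the range further.

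**Month-and-year records.** An eligible vaccine in the same month as Day 1 needs a gap of at least 29 days. That is possible only with Day 1 on the 30th (vaccine on the 1st) or the 31st (vaccine on the 1st or 2nd). This branch is nearly empty for eligible participants; the year-only branch is the one that matters.

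**Number affected.** Not in the documents. For assumed shares of 1900 participants: 0.5% gives 9.5 (about 10), 1% gives 19, 3% gives 57.

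Appendix C does not say whether the injection means Day 1 or Day 22. When the years match, either reading puts the vaccine on a study injection day.

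**The case against.** Several points on the other side stand.

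- Protocol 6.9 asks for start and end dates of administration. A complete pre-injection end date switches the exception off, so the rule does not fire on every vaccine record.
- Sites must establish vaccine timing to confirm eligibility, which should limit year-only dates.
- Dating to the injection is a consistent convention across Appendices C, D and E, and the affected outputs are descriptive, with no hypothesis test.
- Protocol 6.9.2 collects non-study vaccinations from 28 days before injection, while the schedule lists vaccination history as a separate screening item. The documents do not show whether an older vaccine enters the vaccination-only rows or just the combined rows.
- Imputing the first day of the year has its own error: it would hide a vaccine in fact given within 28 days before Day 1.

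A reader might also infer that the false dates remove valid participants from the PP Set. Protocol 6.9.3 lists a non-study vaccine within 28 days before to 21 days after an injection, and also "Nonstudy influenza or RSV vaccine at any time during the study", as possible grounds for exclusion, and IcEv2 is similar. The documents do not support that step. SAP 6.2.7 has the sponsor determine and document PP exclusions before database lock and unblinding, and nothing says that imputed dates feed that decision. Vaccines given before Day 1 also precede randomization, so no imbalance between arms would be expected.

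None of this corrects the status of a same-year, year-only vaccine that is already known to precede Day 1.

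**Conclusion.** The concern holds as a minor defect in the date-imputation rules. A vaccine recorded with only the year, or only the month and year, of the injection, and without a complete pre-injection end date, is dated to the injection day even if it was reported at screening as given earlier. It is then counted as concomitant in the 7-day and 21-day summaries. The established effect is false entries in descriptive tables.

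The size is unknown. The range of about 10 to 57 participants rests wholly on the assumed 0.5% to 3%. Records with an earlier calendar year are not re-dated. No effect on the PP Set or on the coprimary analyses is shown.

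**What to change.** Add a vaccine paragraph to Appendix C:

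1. A single-day vaccination whose record shows that it was given before Day 1 is exempt from the injection-date exception. It stays prior, its imputed date lies before Day 1, and its stop date equals its start date.
2. A vaccine first reported after Day 1 keeps the current conservative rule.
3. Imputed dates are not used to decide whether a vaccine fell in the 28-day pre-injection window, or to apply protocol 6.9.3 or IcEv2. The site is queried for the date.

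Item 3 prevents item 1 from hiding a recent vaccine, and settles in writing a question that SAP 6.2.7 leaves open. The cost is a few site queries and a small change to the concomitant-medication derivation.

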9.4. Appendix D Imputation Rules for Missing Dates of Procedures/Surgeries

Imputation rules for missing or partial dates of procedures/surgeries are defined below:

- If only Day is missing, use the first day of the month, unless the start month and year of the procedure/surgery coincide with the start month and year of the injection, in this case, use the date of the injection.
- If Day and Month are both missing, use the first day of the year, unless the start year of the procedure/surgery coincide with the start year of the injection, in this case, use the date of the injection.

• If Day, Month, and Year are all missing, the date will not be imputed, but the procedure/surgery will be treated as concomitant.

9.5. Appendix E Imputation Rules for Missing Dates of AEs

Imputation rules for missing or partial start dates and stop dates of AEs are defined below:

- 1. Missing or partial start date:
 - If only Day is missing, use the first day of the month, unless:
 - The AE end date is on/after the date of the injection or is missing/partial AND the start month and year of the AE coincide with the start month and year of the injection. In this case, use the date of the injection.
 - If Day and Month are both missing, use the first day of the year, unless:
 - The AE end date is on/after the date of the injection or is missing/partial AND the start year of the AE coincides with the start year of the injection. In this case, use the date of the injection.
 - If Day, Month, and Year are all missing, the date will not be imputed. However, if the AE end date is prior to the date of the injection, then the AE will be considered a pretreatment AE and will not be included in the AE analyses. Otherwise, the AE will be included in the AE analyses.
- 2. Missing or partial end dates will not be imputed.

9.6. Appendix F Schedule of Activities

Study Period	Screening	Inter	vention P	eriod		Foll	ow-up	
Visit Number	Screening	1	2	3	4	5	6	7
Visit Month*	-1	1	1	1	1	2	3	6
Visit Day	Screeninga	D1 ^a	D8	D22	D29	D43 ^b	D91	D202/ EoS
Window Allowance (Days)	-28	N/A	+3	+7	+3	-2 to +7	±5	±14
Type of Visit	V	V	SC	V	SC	V	SC	SC
Informed consent, demographics, concomitant medications and vaccinations, and medical history	X	-	_	_	-	-	-	-
Inclusion/exclusion criteria	X	X	_	=	_	-	-	=
Physical examination ^c	X	X	_	X	-	-	-	-
Vital sign measurements ^d	X	X	_	X	-	-	-	-
Randomization	-	X	-	-	-	-	-	-
Blood sample collection for humoral immunogenicity ^e	-	X	_	X	-	X	-	-
Study vaccination (including a 30-minute postdose observation period) ^{d,f}	-	X	-	X	-	_	-	-
eDiary activation for recording solicited ARs (7 days)g	_	X	_	X	_	-	_	_
eDiary review ^g		X	X	X	X			
Follow-up safety telephone call ^h	_	-	X	_	X	-	X	X
Recording of unsolicited AEs	-	X	X	X	X	X	_	_
Concomitant medications ⁱ	_	X	X	X	X	X	_	_
Recording of SAEs, AESIs, MAAEs, AEs leading to discontinuation, and concomitant medications relevant to or for their treatment ^h	-	X	X	X	X	X	X	X

Study Period	Screening	Inter	vention P	eriod		Foll	ow-up	
Visit Number	Screening	1	2	3	4	5	6	7
Visit Month*	-1	1	1	1	1	2	3	6
Visit Day	Screeninga	D1 ^a	D8	D22	D29	D43 ^b	D91	D202/ EoS
Window Allowance (Days)	-28	N/A	+3	+7	+3	-2 to +7	±5	±14
Type of Visit	V	V	SC	V	SC	V	SC	SC
Recording of nonstudy vaccinationsh,i	_	X	X	X	X	X	X	X
Study completion	-	-	_	-	-	_	=	X

Abbreviations: AE = adverse event; AESI = adverse event of special interest; AR = adverse reaction; D = Day; eDiary = electronic diary; EoS = end of study; IM = intramuscular; M = month; MAAE = medically attended adverse event; N/A = not applicable; RSV = respiratory syncytial virus; SAE = serious adverse event; SC = safety telephone call; ; V = in-person visit; - = indicated activity not performed on that day.

*A month is defined as 30 days.

Arm 1: Fluzone HD+mRNA-1345 μg on Day 1 followed by placebo (0.9% sodium chloride) on Day 22;

Arm 2: Fluzone HD+placebo (0.9% sodium chloride) on Day 1 followed by mRNA-1345 μg on Day 22.

- ^{a.} The Screening Visit and Day 1 Visit may be performed on the same day or on different days (see protocol Section 5.3 for additional details).
- If a participant cannot attend a scheduled in-person visit (with the exception of the Screening Visit, Day 1, and Day 22), a home visit is acceptable if performed by appropriately delegated study clinic staff.
- A complete physical examination, including height and weight, will be performed at the Screening Visit. Symptom-directed physical examinations will be performed at other study visits, if clinically indicated (see protocol Section 8.3.1 for additional details).
- d. Vital sign measurements include assessment of systolic and diastolic blood pressure, pulse rate, respiratory rate, and body temperature (preferred route is oral) (see protocol Section 8.3.2 for additional details).
- Blood samples for humoral immunogenicity must be collected prior to administration of the study intervention on Day 1 and Day 22.
- All participants will be randomized to receive 2 IM injections, one in each arm, in the deltoid muscle (Day 1) and 1 IM injection in the deltoid muscle (Day 22).
- At Day 1 and Day 22, eDiary instruction will be provided while the participant is onsite. The participant will be required to make eDiary entries approximately 30 minutes after each vaccination while at the study site and again that same evening when at home. Study participants will continue to record in the eDiary each day at the same time for 6 days following each vaccination. Local solicited ARs will be recorded separately for each injection. eDiary review by the site should occur daily on Day 1-Day 7 and Day 22-28. Additional review of the eDiary will occur at Day 8 and Day 29 between the site and the participant during the safety telephone calls.
- h. Medically qualified study staff will contact all participants. The participant will be interviewed according to the script. Information will be collected about occurrence of unsolicited AEs through 21 days postvaccination for either RSV or influenza, and the occurrence of MAAEs, SAEs,

Confidential Page 40
Document Number: VV-CLIN-015611 eDMS Version: 2.0

AESIs, or AEs leading to study discontinuation and concomitant medications associated with those events, and receipt of any nonstudy vaccinations at all points of contact.

Date Issued: 10-Nov-2023

All concomitant medications and procedures will be recorded for 21 days following each vaccination (Day 1 through Day 43); all nonstudy vaccinations and concomitant medications relevant to or for the treatment of an SAE, AESI, or MAAE will be recorded from Day 1 through Month 6 after the last study injection/EoS.

9.7. Appendix G Estimands and Estimand Specifications

Table 4: Intercurrent Events

Label	Intercurrent Event Type
IcEv1 (Early discontinuation)	Discontinued early from study.
IcEv2 (Prohibited medications)	Received any concomitant medications and non-study vaccines deemed to affect immune responses.
IcEv3 (Important protocol deviation impacting key study data)	Received a wrong Day 1 study intervention or Day 22 study intervention, enrolled/dosed at two investigational sites, did not have a baseline immunogenicity assessment or did not have any post-injection immunogenicity assessments.
IcEv4 (Immunogenicity assessments falling out of visit window)	Had immunogenicity assessments falling out of analysis visit windows described in Appendix B.

Abbreviation: IcEv: intercurrent event.

Table 5: Summary of Primary Immune Estimands with Rationale for Strategies to Address Intercurrent Events

Objective: To evaluate the impact of coadministered HD quadrivalent seasonal influenza vaccine on the immune response to mRNA-1345 RSV vaccine against RSV-A and RSV-B			
Estimand Label	Primary Immune Estimand 1a (on the PP Set)	Supportive Immune Estimand 1b (on the FAS Set)	
Estimand Description	Immune response to mRNA-1345 RSV vaccine measured as GMR of RSV-A and RSV-B nAbs at Day 22 (Arm 1) or Day 43 (Arm 2) in adults ≥65 years old who receive the assigned study intervention dose at both Day 1 and Day 22, comply with immunogenicity blood sampling to have a baseline and at least 1 postinjection assessment, and have no important protocol deviations impacting the immune response.	Immune response to mRNA-1345 RSV vaccine measured as GMR of RSV-A and RSV-B nAbs at Day 22 (Arm 1) or Day 43 (Arm 2) in adults ≥65 years old who receive any study intervention dose irrespective of any important protocol deviations impacting the immune response.	
Target Population	Adults ≥65 years old who receive the assigned study intervention dose at both Day 1 and Day 22, comply with immunogenicity blood sampling to have a baseline and at least 1 postinjection assessment, and have no important protocol deviations impacting the immune response.	Adults ≥65 years old who receive any study intervention dose irrespective of any important protocol deviations impacting immune response.	
Endpoint	GMT of serum RSV-A and RSV-B nAbs at Day 22 (Arm 1) or Day 43 (Arm 2).	As per Estimand 1a.	
Treatment Conditions	Fluzone HD + mRNA-1345/Placebo (Test) vs. Fluzone HD + Placebo/mRNA-1345 (Reference)	As per Estimand 1a.	

Population-Level Summary	Immune response to mRNA-1345 RSV vaccine defined as GMR of RSV-A and RSV-B nAbs using an ANCOVA model on the log-transformed tiers at Day 22 (Arm 1) or Day 43 (Arm 2), with the treatment group as a fixed variable, adjusted for stratified age group used for randomization and log-transformed baseline tiers.	As per Estimand 1a.
Intercurrent Event Strategy		
IcEv1 (Early discontinuation)	Treatment policy (Including all data collected)	Treatment policy (Including all data collected)
IcEv2 (Prohibited medications)	Principal stratum (Excluding participants)	Treatment policy (Including all data collected)
IcEv3 (Important protocol deviation impacting key study data)	Principal stratum (Excluding participants)	Treatment policy (Including all data collected)
IcEv4 (Immunogenicity assessments falling out of visit window)	Hypothetical (Excluding related data)	Treatment policy (Including all data collected)
Rationale for Strategies	This estimand seeks to understand immune response impact during the coadministered HD quadrivalent seasonal influenza vaccine in adults aged 65 or older who receive the assigned study intervention dose at both Day 1 and Day 22 and comply with key protocol criteria. A principal stratum is used to exclude participants with prohibited medications affecting immune responses or important protocol deviations impacting key study data so that analysis is a sub-population composed of participants free from such intercurrent events. For early discontinuation, all collected data are included. Immunogenicity assessments falling out of visit window are excluded.	A treatment policy strategy is used for following up immune response including all participants who receive any study intervention dose irrespective of whether they subsequently were found not to strictly meet the key protocol criteria. There is interest in understanding immune response in the light of poor compliance which may happen in clinical practice.
	impact of coadministered mRNA-1345 RSV vaccine on that vaccine-matched influenza A and B strains	ne immune response to HD quadrivalent seasonal
Estimand Label	Primary Immune Estimand 2a (on the PP Set)	Supportive Immune Estimand 2b (on the FAS Set)

Estimand Description	Immune response to HD quadrivalent seasonal influenza vaccine measured as GMR of anti-HA Abs as measured by HAI assay at Day 22 in adults ≥65 years old who receive the assigned study intervention dose at both Day 1 and Day 22, comply with immunogenicity blood sampling to have a baseline and at least 1 postinjection assessment, and have no important protocol deviations impacting the immune response.	Immune response to HD quadrivalent seasonal influenza measured vaccine as GMR of anti-HA Abs as measured by HAI assay at Day 22 in adults ≥65 years old who receive study intervention dose irrespective of any important protocol deviations impacting the immune response.
Target Population	Adults ≥65 years old who receive the assigned study intervention dose at both Day 1 and Day 22, comply with immunogenicity blood sampling to have a baseline and at least 1 postinjection assessment, and have no important protocol deviations impacting the immune response.	Adults ≥65 years old who receive any study intervention dose irrespective of any important protocol deviations impacting immune response.
Endpoint	GMT of serum anti-HA Abs by HAI assay at Day 22.	As per Estimand 2a.
Treatment Conditions	Fluzone HD + mRNA-1345/Placebo (Test) vs. Fluzone HD + Placebo/mRNA-1345 (Reference)	As per Estimand 2a.
Population-Level Summary	Immune response to HD quadrivalent seasonal influenza vaccine defined as GMR anti-HA Abs by HAI assay using an ANCOVA model on the log-transformed tiers at Day 22, with the treatment group as the fixed variable, adjusted for stratified age group used for randomization and log-transformed baseline tiers.	As per Estimand 2a.
Intercurrent Event Strategy		
IcEv1 (Early discontinuation)	Treatment policy (Including all data collected)	Treatment policy (Including all data collected)
IcEv2 (Prohibited medications)	Principal stratum (Excluding participants)	Treatment policy (Including all data collected)
IcEv3 (Important protocol deviation impacting key study data))	Principal stratum (Excluding participants)	Treatment policy (Including all data collected)
IcEv4 (Immunogenicity assessments falling out of visit window)	Hypothetical (Excluding related data)	Treatment policy (Including all data collected)

Rationale for Strategies	This estimand seeks to understand immune response impact during the coadministered HD quadrivalent seasonal influenza vaccine in adults aged 65 or older who receive the assigned intervention dose at both Day 1 and Day 22 and comply with key protocol criteria. A principal stratum is used to exclude participants with prohibited medications affecting immune responses or important protocol deviations impacting key study data so that analysis is a sub-population composed of participants free from such intercurrent events. For early discontinuation, all collected data are included. Immunogenicity assessments falling out of visit window are excluded.	A treatment policy strategy is used for following up immune response including all participants who receive any study intervention dose irrespective of whether they subsequently were found not to strictly meet the key protocol criteria. There is interest in understanding immune response in the light of poor compliance which may happen in clinical practice.
--------------------------	---	--

Table 6: Summary of Primary Safety Estimands with Rationale for Strategies to Address Intercurrent Events

Objective: To evalua vaccine (Fluzone® H	te the safety and tolerability of mRNA-1345 RSV vaccine cosID)	administered with a HD quadrivalent seasonal influenza
Estimand Label	Safety Estimand 3a	Safety Estimand 3b
Estimand Description	Proportion of participants reporting any solicited local ARs up to 7 days after each study injection (Day 1 or Day 22).	Proportion of participants reporting any unsolicited AEs up to 21 days after each study injection (Day 1 or Day 22).
	• Proportion of participants reporting any solicited systemic ARs up to 7 days after each study injection	 Proportion of participants reporting any MAAEs up to Day 202/EOS.
	(Day 1 or Day 22).	 Proportion of participants reporting any AESI up to Day 202/EOS.
		 Proportion of participants reporting any SAEs up to Day 202/EOS.
		 Proportion of participants reporting any AEs leading to discontinuation from the study up to Day 202/EOS.
Target Population	Adults ≥65 years old who receive any study intervention and contribute any solicited AR data.	Adults ≥65 years old who receive any study intervention.
Endpoint	• Incidence of solicited local ARs up to 7 days after each study injection.	Incidence of unsolicited AEs up to 21 days after each study injection.
	• Incidence of solicited systemic ARs up to 7 days after	 Incidence of MAAEs up to Day 202/EOS.
	each study injection.	 Incidence of AESI up to Day 202/EOS.
		 Incidence of SAEs up to Day 202/EOS.
		Incidence of AEs leading to discontinuation from the study up to Day 202/EOS.
Treatment	Fluzone HD + mRNA-1345/Placebo (Test) vs.	Same as Estimand 3a.
Conditions	Fluzone HD + Placebo/mRNA-1345 (Reference)	

Population-Level Summary	 Proportion of participants reporting any solicited local ARs up to 7 days after each study injection by treatment group. Proportion of participants reporting any solicited systemic ARs up to 7 days after each study injection by treatment group. 	 Proportion of participants reporting any unsolicited AEs up to 21 days after each study injection by treatment group. Proportion of participants reporting any MAAEs up to Day 202/EOS by treatment group. Proportion of participants reporting any AESI up to Day 202/EOS by treatment group. Proportion of participants reporting any SAEs up to Day 202/EOS by treatment group.
Intercurrent Event Strategy		
IcEv1 - IcEv4	Treatment Policy (Including all data collected)	Treatment Policy (Including all data collected)
Rationale for Strategies	Count all relevant safety events observed, irrespective of non	-compliance of key protocol criteria.

